5.4.1 Primary Efficacy Analyses

The rate of subjects whose best overall response is CR or PR is calculated as ORR, and the Exact 95% CI is also calculated. Analysis based on central assessment by Efficacy and safety evaluation committee will be regarded as primary result.

Additionally, For PTCL, best overall response and ORR using overall response evaluated according to "Revised response criteria for malignant lymphoma" will be summarized. And for CTCL, best overall response and ORR based on global response score of "Clinical end points and response criteria in mycosis fungoides and Sézary syndrome" will be summarized.

5.4.2 Secondary Efficacy Analyses

• Analysis of PFS

PFS will be summarized by Kaplan-Meier method using median with 95% CI. Kaplan-Meier curve will be provided. The number of event/censor (percentage) will be also summarized.

• Analysis of DOR

DOR will be summarized by Kaplan-Meier method using median with 95% CI in responders. The number of event/censor (percentage) will be also summarized.

• Analysis of TTR

TTR will be summarized using descriptive statistics in responders.

• Analysis of CR rate

Best overall response will be summarized. For CR rate (the rate of subjects whose best overall response is CR) Exact 95% CI will also be provided.

• Analysis of OS

OS will be summarized by Kaplan-Meier method using median with 95% CI. Kaplan-Meier curve will be provided. The number of event/censor (percentage) will be also summarized. In addition, summarization for follow-up time will be provided using Kaplan-Meier method.

PFS will be calculated as: End date for PFS – Date of administration of the first dose of study drug + 1 (day) DOR will be calculated as: End date for DOR – Date of the first response + 1 (day)

End date of PFS and DOR is defined as the table below:

Situation	End Date for PFS and DOR	Censored
Documented progression disease (PD) during the study	Date of the first assessment of the series of the tests that determined PD	No
Death during the study before PD	Date of death	No
No baseline assessments	Date of administration of the first dose of study drug	Yes
Treatment discontinuation without post- baseline tumor assessments	Date of administration of the first dose of study drug	Yes
New anticancer treatment started prior to disease progression	Date of last tumor assessment before start of new treatment	Yes
Death or PD after more than one missed tumor assessments	Date of the last tumor assessment before missed assessments	Yes
Subjects still on treatment without PD as of data cut-off	Date of last tumor assessment	Yes

TTR will be calculated as: Date of first response – Date of administration of the first dose of study drug + 1 (day)

OS will be calculated as: End date for OS – Date of administration of the first dose of study drug + 1 (day)

End date for OS is defined as the table below:

Situation	End Date for OS	Censored
Death during the study	Date of death	No
Alive at cut-off	Date of cut-off	Yes
Other than the above	Last known alive date	Yes

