3.2 Overall Study Design and Plan

This is a multicenter, single-arm, open label, Phase 2 to evaluate efficacy, safety, PK and immunogenicity of E7777 in patients with relapsed or refractory PTCL and CTCL. This study composed of the following 3 periods: preparation, treatment and follow-up periods. The preparation period consists of the following four procedures: informed consent (IC), screening, enrollment, and baseline assessment. Informed consent (IC) is able to obtain 28 days before the treatment. Enroll the patient who meet the inclusion criteria and does not meet the exclusion criteria. Conduct the baseline assessment within 7 days before the treatment. Confirm that the patient continue to meet the inclusion criteria and does not meet the exclusion criteria before moving to the treatment period. The

treatment period consists of 1 cycle of 3 weeks and lasts until meet the "discontinuation criteria" or Day 21 of Cycle 8. The evaluation at discontinuation will be performed within 7 days after termination of study treatment.

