4 DETERMINATION OF SAMPLE SIZE

Thirty-five patients were required to detect lower limit of the 95% confidence interval (CI) that exceed the 5% threshold in ORR, which is the primary endpoint of the study, with the expected ORR is 25% with a statistical power of 90%. In CTCL, 6 or more patient is targeted to evaluate the safety as specific disease.

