5.2 Study Subjects

5.2.1 Definitions of Analysis Sets

Full Analysis Set (FAS):

Defined as a group of subjects who have received at least one dose of the study drug. This group will be the population for the evaluation of efficacy.

Safety Analysis Set:

Defined as a group of subjects who have received at least one dose of the study drug with at least one evaluable post-baseline safety data. This group will be the population for the evaluation of safety.

Pharmacokinetics Analysis Set:

Defined as a group of subjects in who have received at least one dose of the study drug with at least one serum concentration data.

Pharmacodynamics Analysis Set:

Defined as a group of subjects in who have received at least one dose of the study drug with at least one evaluable pre and post-baseline PD data.

On eligibility-confirmed subjects, the number (percentage) of subjects included in each analysis set will be summarized.

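### The PFS table both counts and censors the same early death: a subject who stops treatment and dies without a post-baseline scan meets an event row and a Day-1 censoring row, with no stated precedence.

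*SAP*

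**What the plan says.** The table in SAP Section 5.4.2 sets the end date and censoring status for PFS and DOR. Five of its rows matter here:

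- **Death row:** "Death during the study before PD" is an event, dated at death.
- **Discontinuation row:** "Treatment discontinuation without post- baseline tumor assessments" is censored at the date of first dose.
- **No-baseline row:** "No baseline assessments" is also censored at the date of first dose.
- **New-treatment row:** "New anticancer treatment started prior to disease progression" is censored at the last tumor assessment before the new treatment.
- **Missed-assessment row:** "Death or PD after more than one missed tumor assessments" is censored at the last assessment before the gap.

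PFS is the end date minus the first-dose date plus 1, so censoring at first dose gives a PFS of 1 day. The text introducing the table gives no order of precedence. Neither do Sections 5.3.5 and 8.2, which say only that missing data are not imputed.

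PFS is analysed in the FAS, "Defined as a group of subjects who have received at least one dose of the study drug", so no post-baseline scan is needed to be included. Section 5.4 calls for all efficacy results by disease as well as overall.

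**The concern.** Neither first-dose censoring row is limited to subjects who are alive. A subject who receives a dose, stops treatment and dies during the study before any post-baseline scan satisfies the death row and the discontinuation row together. One makes the subject an event at death; the other removes the subject on Day 1.

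The case can occur. Section 3.2 makes follow-up one of the three study periods, so a death after discontinuation can fall within the study. Section 5.4 exempts PFS and DOR from the rule that limits tumor assessments to those before treatment discontinuation.

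The no-baseline row overlaps with the death row in the same way. Such subjects should be rare, because Section 3.2 says "Conduct the baseline assessment within 7 days before the treatment".

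If the censoring rows are applied as written, subjects leave the risk set on Day 1 because they did badly. That is informative censoring, and it can only raise the PFS curve. If the choice is left open until early deaths are known, it is made with sight of the data in an open-label, single-arm trial.

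**Working it through.** **Does row order settle it?**

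- *Top row wins.* The death is an event. But then the missed-assessment row never acts, because the progression and death rows have already taken every case it describes. The new-treatment row could likewise never censor a subject who later progressed or died.
- *Bottom row wins.* The death is censored on Day 1. But the SAP nowhere says that later rows override earlier ones.

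**Does giving every row an effect settle it?** No. Two schemes do so:

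- The new-treatment and missed-assessment rows are exceptions to the event rows, and the two first-dose rows apply only to subjects without an event. The death is then an event.
- All censoring rows are exceptions to the event rows. The death is then censored on Day 1.

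**Size.** The SAP states no figure for PFS. The only planned figures used are n = 35 overall and the CTCL target of 6, both from Section 4 ("In CTCL, 6 or more patient is targeted to evaluate the safety as specific disease"). The number k of affected deaths is an assumption. Take k deaths before the first scan, with no earlier exits.

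- Early PFS (after the k deaths, before any other event): (35 − k)/35 with deaths as events; 100% with Day-1 censoring.
- After that point both codings have the same risk set, so every later estimate is inflated by 35/(35 − k).
- Example: a true later value of 20/35 = 57.1% becomes 20/(35 − k).
- Median, taken as the first time the estimate is at or below 50%, with all other subjects having distinct later events and no other censoring: the 18th of the 35 ordered times with deaths as events, since 35/2 = 17.5; position k + ceil((35 − k)/2) with Day-1 censoring.

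| k | Early PFS, deaths as events | Early PFS, Day-1 censoring | Later inflation | 57.1% becomes | Shift (points) | Median position, event vs Day-1 |
|---|---|---|---|---|---|---|
| 1 | 34/35 = 97.1% | 100% | 35/34 = 1.029 | 20/34 = 58.8% | 1.7 | 18th vs 18th |
| 2 | 33/35 = 94.3% | 100% | 35/33 = 1.061 | 20/33 = 60.6% | 3.5 | 18th vs 19th |
| 4 | 31/35 = 88.6% | 100% | 35/31 = 1.129 | 20/31 = 64.5% | 7.4 | 18th vs 20th |

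For scale, the binomial standard error at 57.1% is sqrt(0.571 × 0.429 / 35) = 8.4 points. The event and censoring counts, which Section 5.4.2 also reports, each change by k.

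**CTCL, if only 6 are enrolled and k = 1:**

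- Early PFS is 5/6 = 83.3% against 100%.
- Later estimates are inflated by 6/5 = 1.20.
- The median moves from the 3rd time (6/2) to the 4th (1 + ceil(5/2)).

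**Endpoints not touched.** ORR uses best overall response, and OS has its own end-date table. The post-baseline overlap cannot reach DOR, because a responder must have had a post-baseline assessment.

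**The case against.** The strongest reply is that the table is readable as it stands. Where it means to censor a death, in the missed-assessment row, it names death; the discontinuation row does not. Reading the first-dose rows as covering only subjects without an event makes the table coherent, and upward bias arises only under the less natural reading. **This stands as a reason to expect the right coding, but it does not exclude the other one.** The missed-assessment row shows that this table does let a censoring row override a death.

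Section 9 places derivation rules in separate documents, and the protocol is not at hand, so precedence may be set elsewhere. **That is possible.** But the SAP prints its own censoring table, and Section 7 records that the PFS and DOR censoring rule was changed. Whether a death counts as an event changes the result and belongs in that table.

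The affected group is narrow. Section 3.2 also schedules an evaluation within 7 days of stopping treatment; if that includes a tumor assessment, there are fewer cases. **This stands**, and it bears on k, not on the overlap.

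The effect is modest: every overall shift shown is below one standard error, and PFS carries no test. **This also stands.** The median positions depend on the convention. If an estimate of exactly 50% is resolved by a midpoint, the CTCL median with deaths as events lies between the 3rd and 4th times. A median from 6 subjects says little in any case.

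Lastly, the remedy leaves some unscanned deaths censored on Day 1, where the new-treatment or missed-assessment row applies. **True**, but that follows the SAP's own explicit choice in those rows, which is a separate question.

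**Conclusion.** The contradiction is real and should be fixed before the data are analysed. Two rows assign opposite event status and different end dates to the same subject, and the SAP gives no rule to choose between them. Death as an event is the likelier intention. The other reading is permitted by the text and always favours the drug.

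Confidence in the overlap is high. The size is illustrative: it rests on an assumed 1, 2 or 4 such deaths among 35, before the first scan and with no earlier exits. On that basis a later PFS of 57.1% is overstated by 1.7 to 7.4 points, and the overall median moves by at most two positions. One such death among 6 CTCL subjects inflates later PFS estimates in that group by 20%. The consequence is confined to a secondary, descriptive endpoint.

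**What to change.** In the Section 5.4.2 table, limit the no-baseline row and the discontinuation row to subjects with no death during the study. Then add one sentence with this content:

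- Death before progression is a PFS event on the date of death, even without a baseline or post-baseline tumor assessment, unless the new-treatment row or the missed-assessment row applies.
- Under those two rows, the end date is the first-dose date when there is no post-baseline assessment. Without this, a baseline scan dated before first dose would give a PFS of zero or less under the SAP's formula.

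It would also help to state whether assessments not done after treatment stops count as missed, since that decides which unscanned deaths fall under the missed-assessment row.

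The cost is two edited rows and one sentence, with no extra data. Reported PFS may be slightly less favourable.

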5.3 Data Analysis General Considerations

All efficacy analyses will be conducted based on FAS.

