5.4 Efficacy Analyses

FAS will be the primary analysis population. All efficacy result will be summarized for each disease and overall. Results from central assessment by efficacy and safety evaluation committee and investigator assessment will be used, as applicable. If needed, efficacy analysis results per investigator assessment will also be summarized. Unless otherwise noted, overall response considering both "Revised Response Criteria for Malignant Lymphoma (Cheson, J Clin Oncol; 2007)" and "Clinical Endpoints and Response Criteria in Mycosis Fungoides and Sézary Syndrome (Olsen, J Clin Oncol; 2011)" will be used.

For summarization of tumor assessment relevant analysis except PFS and DOR, assessment results until discontinuation from study treatment will be used.

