7 CHANGES IN THE PLANNED ANALYSES

The list below includes both change from protocol and SAP version 1.0.

- Summarization of "Analysis Sets" has been added (section 5.2.1).
- Summarization of "Completion and discontinuation for treatment" has been deleted because the data is not collected (section 5.2.2).
- Summarization of "CCR4 category", "each disease histology and each stage" and "Relapsed/Refractory status" has been added (section 5.2.3).
- Summarization of "Number of previous systemic chemotherapy regimen" and "each previous systemic chemotherapy" has been added (section 5.2.4).
- Summarization of "prior medication" and "concomitant medication" has been deleted (section 5.2.4).
- Definition of concomitant medication has been changed (section 5.2.4).
- Summarization of "Treatment Compliance" has been added (section 5.2.5).
- Subgroup analyses for efficacy and safety have been added (section 5.3.4).
- Summarization of efficacy endpoints by investigator has been added (section 5.4).
- Handling rule of tumor assessment data has been clarified (section 5.4).
- Summarization of "BOR and ORR focused on PTCL/CTCL evaluation criteris" has been added (section 5.4.1).
- Summarization of "Event/censor" for PFS, DOR and OS has been added (section 5.4.2).
- Kaplan-Meier curve for PFS, OS and OS has been added (section 5.4.2).
- Censoring rule for PFS and DOR has been changed (section 5.4.2).
- Summarization of TTR has been changed to not use Kaplan-Meier method because there is no need to use Kaplan-Meier method if the target is responder. (section 5.4.2).
- Summarization of "Best overall response" has been added (section 5.4.2).

- Summarization of "Best overall response and ORR for each disease histology" has been added (section 5.4.3).
- Summarization of "Best response for each lesion" has been added (section 5.4.3).
- Waterfall plot of "target lesions and mSWAT score" has been added (section 5.4.3).
- Spider plot of "target lesions and mSWAT score" has been added (section 5.4.3).
- Plotting individual values of immunogenity titer and PD markers on mean plot has been deleted (section 5.5.2).
- Summarization of "dose ratio" has been changed to "relative dose intensity" (section 5.6.1).
- Definition of TEAEs has been changed to be conservative (section 5.6.1).
- Detailed listing of AE tables has been added (section 5.6.2).
- Some patterns of summazation on TEAEs has been added (section 5.6.2).

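### Does the PFS/DOR end-date table leave event-free subjects who are off treatment without a censoring date?

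*SAP*

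**What the plan says.** SAP section 5.4.2 defines the end date for PFS and DOR by a table of seven situations.

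- Two are events: "Documented progression disease (PD) during the study", and death in the study before progression.
- Two censor at the first dose: no baseline assessment, and stopping treatment with no post-baseline assessment.
- Two censor at an earlier tumor assessment: new anticancer therapy before progression, and death or progression after more than one missed assessment.
- The last, "Subjects still on treatment without PD as of data cut-off", censors at the last tumor assessment.

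Four other places bear on this.

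- Section 3.2: the study has a follow-up period, and treatment "lasts until meet the 'discontinuation criteria' or Day 21 of Cycle 8".
- Section 5.4: "For summarization of tumor assessment relevant analysis except PFS and DOR, assessment results until discontinuation from study treatment will be used".
- Sections 5.2.1 and 5.3: of the FAS, "This group will be the population for the evaluation of efficacy", and "All efficacy analyses will be conducted based on FAS".
- Section 5.4.2, OS table: it ends with a residual row, "Other than the above". The PFS/DOR table has no such row.

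**The concern.** Events count throughout the study, including follow-up, but the general censoring row is worded for subjects still on treatment. With a treatment course of at most 8 cycles, an event-free subject followed for longer will normally be off treatment. That is the ordinary long responder, and such subjects shape the right-hand side of the DOR curve. The FAS rule requires an end date for each of them, and the table does not literally give one.

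Two errors would matter. If these subjects were left out for want of an end date, median PFS and DOR would be too short. If they were censored at the end of treatment while later progression still counted as an event, censoring would depend on the later outcome. DOR would then be biased short although nobody is missing from the counts. DOR helps in interpreting ORR in a single-arm trial, so the question deserves a check.

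**Working it through.** **Is there a gap?** Take a subject with baseline and post-baseline assessments who is off treatment, alive, without progression and without new therapy. Neither event row applies. Neither first-dose row applies, since both assessments exist. The new-therapy and missed-assessment rows do not apply, and the last row requires ongoing treatment. So no row fits.

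**How often?** The SAP gives no figure for this, so the inputs below are assumptions except where a source is named.

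- Longest treatment without delays: 8 × 21 = 168 days = 24 weeks, about 5.5 months (section 3.2).
- Responders: 25% of 35 = 8.75, taken as 9 (section 4).
- Assumed: exponential duration with median m, so S(t) = 2^(−t/m); F = 12 months of follow-up after response; no new therapy before progression; no loss to follow-up.

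Expected responders matching no row = 9 × S(12):

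- m = 6: 9 × 0.250 = 2.3
- m = 9: 9 × 0.397 = 3.6
- m = 12: 9 × 0.500 = 4.5

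**Which date does the document point to?** The last row has two parts. Being on treatment describes the situation; the end date is simply the last tumor assessment, with no on-treatment limit. For the subjects that row names, the last assessment on treatment and the last overall are the same, so the row cannot favour the on-treatment date for anyone else. The remaining text points one way:

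| Source | What it uses |
|---|---|
| New-therapy row | last assessment before the new therapy, not the last on treatment |
| Missed-assessment row | last assessment before the gap |
| Section 5.4 | PFS and DOR exempt from the cut at treatment discontinuation |
| Both first-dose rows | only where a baseline or post-baseline assessment is lacking |

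Every censoring row for a subject with usable assessments therefore uses a tumor-assessment date, and post-treatment assessments are admitted. The missing case falls to the last tumor assessment overall.

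**What if the hybrid rule were used?** Suppose event-free subjects were censored at end of treatment, c months after response, while progression up to F still counted. For t > c the Kaplan-Meier limit is S(c) × [S(t) − S(F)] / [S(c) − S(F)]. Assuming response at 1.5 months, c = 5.5 − 1.5 = 4.0. For m = 9 and F = 12:

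- S(4) = 2^(−4/9) = 0.735 and S(12) = 2^(−12/9) = 0.397.
- Setting the limit to 0.5: S(t) = 0.397 + 0.5 × (0.735 − 0.397)/0.735 = 0.627.
- t = 9 × log2(1/0.627) = 6.1 months.

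The same steps give 5.2 for m = 6 and 6.6 for m = 12. With F = 18 the three medians are 5.6, 7.1 and 8.0. For PFS (c = 5.5, F = 12) true medians of 3, 4 and 6 months give 3.0, 4.0 and 5.8.

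**What if the subjects were dropped?** This was simulated with 35 subjects, a true median PFS of 180 days, accrual over 180 days, exponential early stopping with mean 300 days, and cut-off 240 or 365 days after last enrolment. About 10.0 or 6.2 subjects match no row. Dropping them moves the typical median from about 178–179 days to 114 or 138.

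Both calculations show the cost of an error. Neither describes what the SAP prescribes: sections 5.2.1 and 5.3 rule out dropping treated subjects, and nothing in the SAP sets an end-of-treatment censoring date.

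**The case for a change.** The strongest case for a change is that the SAP calls this table the definition, that the unmatched subject is common, and that the OS table shows the authors knew how to write a residual row. Section 7 records that the PFS/DOR censoring rule was changed, so the protocol or SAP version 1.0 cannot be assumed to supply the missing line. Section 5.3.5 bars imputation. Rewording one row would cost almost nothing.

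The missing case stands. The claimed conflict does not: the FAS rule says who is analysed, the table is silent on one status, and filling the silence breaches neither. Section 7 does not say which part of the censoring rule changed, so it settles nothing either way. The bar on imputation is no obstacle, because censoring at an observed assessment date imputes nothing. Derivation rules are placed in separate documents (section 9), and data handling is to be decided before database lock (section 8), so there is a regular place for this detail.

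Nor is a quick rewording free of risk. A new last row for everyone alive without progression and without new therapy, on or off treatment, would overlap the two first-dose rows unless it excluded subjects already covered by another row.

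**Conclusion.** The table omits one common status, but the omission is a missing detail that analysts would fill sensibly. The evident date is the last tumor assessment, including those after treatment. Under that reading all FAS subjects are kept, later events and later event-free time are treated alike, and the Kaplan-Meier median estimates the true value, so no result changes. At a true median DOR of 12 months with 12 months of follow-up the median would only just be reached, but that is a limit of follow-up and not of the table.

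The medians of 5.2, 6.1 and 6.6 months against 6, 9 and 12 follow arithmetically, but from a rule the SAP does not contain and from assumed exponential times, response at 1.5 months and uniform follow-up. PFS and DOR are secondary and descriptive, section 5.3.3 plans no statistical comparison, and neither ORR nor the sample size depends on this table. No change to the plan is called for.
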